7.2. EVALUATIONS BY VISIT

7.2.1. Screening Visit 1 (Days -29 to 0)

Patients who completed PTI-125-02 < 60 days of study start will not be rescreened but will sign the ICF on Day 1 or earlier for this open-label extension.

For all other patients, the following will be completed in the screening visit:

- Informed Consent
- Review of Inclusion and Exclusion Criteria
- Medical history
- Review of concomitant medications
- Confirmation that the patient is either fully vaccinated for the COVID-19 virus at least 2 weeks prior to first dose of simufilam, or a positive serology test for the COVID-19 virus with no current symptoms
- If needed, CT scan to confirm I/E criteria, per investigator judgement
- MMSE-2 evaluation (prior patients do not need to meet 16 to 26 range)
- Columbia Suicide Severity Rating Scale (C-SSRS)
- Physical examination, including measurement of vital signs (blood pressure, temperature, pulse and respiratory rate), height, weight
- A 12-lead ECG (5-min supine)
- Laboratory assessments, including serum chemistry, hematology, urinalysis, and screens for HCV, HIV and HBsAg.
- Urine drug screen.

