7.3. LABORATORY ASSESSMENTS

7.3.1. Clinical Laboratory Tests

The following clinical laboratory tests will be performed at screening, Day 1 predose, and at Months 1, 2, 3, 6, 9, 12, 15, 18, 21 and 24:

- Hematology: white blood cell (WBC) count with differential, red blood cell (RBC) count, hemoglobin, hematocrit, platelet count.
- Serum Chemistry: glucose, sodium, potassium, chloride, bicarbonate, calcium, phosphate, blood urea nitrogen (BUN), total bilirubin, creatinine, cholesterol, triglycerides, albumin, globulin, total protein, uric acid, alkaline phosphatase, alanine transaminase (ALT), aspartate transaminase (AST), gamma glutamyl transpeptidase (GGT), lactose dehydrogenase (LDH).
- Urinalysis: color, specific gravity, pH, protein, sugar, ketones, occult blood, creatinine clearance calculation by Cockcroft-Gault equation (without requiring a 24-h urine collection).

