4.7 Safety Analysis

Adverse Events

Treatment emergent AEs (TEAEs), defined as AEs that first occurred or worsened after first dose, will be summarized overall. Summary of TEAEs occuring in the Open-label phase (D1-M12 and M18-M24) will be summarized in one group . TEAEs occurring in Double-blind (RW) phase (M12-M18) will be summarized in other group. All the listings mentioned below to be provided for both the groups. The incidence of TEAEs will be reported as the number (percent) of patients with TEAEs within System Organ Class (SOC) and Preferred Term (PT). Patients will be counted only once within a SOC and PT, even if the patient experienced more than one TEAE within a specific SOC and PT. The number (percent) of patients with TEAEs will also be summarized by maximum severity and relationship. The denominators for calculating the percentages for summaries will be based on the number of patients in the analysis population enrolled to each group.

The following types of summary will be provided for Incidence of TEAEs:

- Treatment Emergent Adverse Events by System Organ Class and Preferred Term;
- Treatment Emergent Adverse Events by System Organ Class, Preferred Term and Maximum Severity;
- Treatment Emergent Adverse Events by System Organ Class, Preferred Term and Relationship to Study Drug;

The annualized incidence rate of AEs per person-years at risk, calculated as (365.25*number of AE occurrences)/(total treatment period with patients at risk of AE), will also be reported by most prevalent PT in the SOC.

The total period at risk for each patient will be defined as the period from first dose of study treatment to the date of the End of Treatment (EOT) (Month 12) or Early Termination (ET) visit for prematurely treatment discontinued patients. Annualized incidence rates will be expressed in terms of events per 100 patient years exposure.

Vital Signs

For Months 6, 12, 18, and 24, summary statistics will be provided (study population size, mean, SD, minimum, median, and maximum) for each vital sign parameter, by treatment group and overall. Summary statistics for change from baseline values will also be presented. Numbers and percentages of patients with abnormal values will be included.

ECG

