The 12-lead ECG tests will be summarized by treatment group and overall using qualitative statistics per each scheduled visit. The summary will include the number and percentage of patients with test values classified as normal, abnormal (clinically significant), abnormal (not clinically significant) and unevaluable.

Laboratory Data

For months 6. 12, 18, and 24, summary statistics will be provided (study population size, mean, SD, minimum, median, and maximum) for each laboratory test and their change from baseline by treatment group and overall, along with their change from baseline screening values will be presented overall, for each scheduled visit. Numbers and percentages of patients with abnormal values will be included.

Physical Examination

Full physical examination data will be listed overall, by enrollment group and patient only.

5 Analysis of Open-Label Phase

The following efficacy analyses will be applied to data from the OL phase (D1-M12).

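### SAP 4.7 counts abnormal laboratory, vital-sign and ECG results without regard to pre-dose status, so abnormalities present at entry are mixed with new ones

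*SAP*

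**What the plan says.** SAP 4.7 plans three categorical safety outputs besides adverse events:

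- Vital signs and laboratory tests, each summarised at Months 6, 12, 18 and 24, carry the same sentence: "Numbers and percentages of patients with abnormal values will be included".
- ECG is "summarized by treatment group and overall using qualitative statistics per each scheduled visit", as the "number and percentage of patients with test values classified as normal, abnormal (clinically significant), abnormal (not clinically significant) and unevaluable".

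The outputs that do refer to a starting value are summary statistics. For vital signs: "Summary statistics for change from baseline values will also be presented". For laboratory tests, summaries are given "for each laboratory test and their change from baseline by treatment group and overall", and the same sentence then adds that "their change from baseline screening values will be presented overall, for each scheduled visit". ECG has no output relative to baseline. SAP 4.7 defines treatment emergence for adverse events only. Protocol 10.4 adds descriptive change from screening for vital signs and laboratory results. Neither document plans a shift table or a count of newly abnormal patients.

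On what may be present at entry, Protocol 5.3 excludes clinically significant laboratory results (criterion 9), ALT, AST or bilirubin above the upper limit if also judged clinically significant (16), and clinically significant ECG abnormality, including QTc limits (21).

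On the samples available, Protocol 7.3.1 states that laboratory tests "will be performed at screening, Day 1 predose, and at Months 1, 2, 3, 6, 9, 12, 15, 18, 21 and 24". Protocol 7.2.1 states that recent PTI-125-02 completers "will not be rescreened but will sign the ICF on Day 1 or earlier".

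**The concern.** A patient who entered with an out-of-range but acceptable result, and still has it at Month 12, adds one to the abnormal count. So does a patient whose result was normal on Day 1 and became abnormal on study. The planned percentage does not tell them apart.

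This matters because SAP 1.3 makes long-term safety and tolerability the overall objective. The first 12 months have no control arm, so the patient's own pre-dose value is the natural reference there. Laboratory abnormality is also a live question for this drug by the protocol's own account: Protocol 2.2 reports adverse liver findings with raised ALP and bilirubin in the 6-month rat study, and Protocol 7.1 sets liver chemistry stopping criteria. In the randomized-withdrawal phase, carried-over abnormality adds a similar amount to both arms and pulls the ratio between them towards 1.

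**Working it through.** The documents state no figure on this point, so there is nothing to reproduce. The check has a textual part and an illustration.

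**Text.** Setting SAP 4.7 beside Protocol 5.3 gives three facts. Non-significant abnormality may be present at entry. None of the three abnormal counts is conditioned on pre-dose status. No other planned table counts patients moving from normal to abnormal. That baseline status is ignored is read from silence, but it is the plain reading.

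**Comparison of two arms.** Let b be the share abnormal at the reference, s the share of those still abnormal at the visit, and e the share newly abnormal among those normal at the reference. All three are assumptions.

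Observed percent = b·s + (1 − b)·e

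With e = 12% versus 5% (ratio 12/5 = 2.4, difference 7.0 points) and s = 1:

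| b | Observed percentages | Ratio | Difference (points) |
|---|---|---|---|
| 2% | 0.02 + 0.98 × 0.12 = 13.8%; 0.02 + 0.98 × 0.05 = 6.9% | 1.99 | 6.9 |
| 20% | 0.20 + 0.80 × 0.12 = 29.6%; 0.20 + 0.80 × 0.05 = 24.0% | 1.23 | 5.6 |
| 40% | 0.40 + 0.60 × 0.12 = 47.2%; 0.40 + 0.60 × 0.05 = 43.0% | 1.10 | 4.2 |

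If only 80% persist (s = 0.8), b = 20% gives 25.6% versus 20.0% (1.28) and b = 40% gives 39.2% versus 35.0% (1.12). Partial persistence changes little. Prevalence drives the result.

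**Single-arm reading.** With e = 5% and s = 0.8:

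| b | Observed | New part, (1 − b)·e | New part as share of count |
|---|---|---|---|
| 2% | 6.5% | 4.9% | 75% |
| 10% | 12.5% | 4.5% | 36% |
| 20% | 20.0% | 4.0% | 20% |
| 30% | 27.5% | 3.5% | 13% |

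Applied for scale to the 220 enrolled (SAP 2.5), b = 20% gives 44 patients counted abnormal, of whom about 9 are new. A count limited to patients normal at reference would show 5% in every row.

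**Reference value.** SAP 4.7 does not define the safety baseline. The definition in SAP 5.1 (last non-missing value on or before Day 1) stands under efficacy. It would not serve vital signs as worded, because Protocol 7.2.3 takes them on Day 1 both before dosing and up to 2 h after. For the randomized phase, Protocol 7.2.9 and Appendix A show no laboratory tests, vital signs or ECG at Withdrawal Day 1, so Month 12 is normally the last value available.

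**The case against.** The plan is not blind to new abnormality, and the case for leaving it alone has several sound parts.

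- Protocol 9.1 makes new clinically significant laboratory, physiological or examination findings adverse events, and SAP 4.7 tabulates those that first occur or worsen after first dose. That is a planned emergent output. It stands, but depends on investigator judgement.
- Laboratory and vital-sign tables give change from baseline. True, but mean, SD, median, minimum and maximum do not say how many patients crossed a limit.
- ECG categories at each scheduled visit include Day 1, so pre-dose prevalence will be visible. True, but marginal percentages at two visits do not show who changed, and 43 patients dropped out in the open-label phase (SAP 2.5).
- Clinically significant abnormality is excluded at entry, so the clinically significant ECG row should be close to emergent. This stands. The problem lies mainly in the other abnormal ECG row and in out-of-range laboratory and vital-sign values.
- Individual shifts could be recovered from the listings. True, but that leaves the reader to build the table.
- At low prevalence the distortion is small, and differences shrink less than ratios. Both stand, as the first table shows.

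A reader might also infer from the word screening that patients who were not rescreened drop out of the laboratory change tables. The documents do not support that. The same sentence first names change from baseline, and a Day 1 pre-dose sample is scheduled for all. At most, those patients would be missing from the added screening-based summary. Their number is not given: it lies between 0 and the 64 enrolled in the earlier placebo-controlled trial (Protocol 2.3.3), and 64/220 = 29% is only an upper bound.

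**Conclusion.** The point holds for the abnormal-value counts. As planned, they mix abnormality allowed at entry, mainly results not judged clinically significant, with abnormality that arose on study. The other planned outputs cover this only in part.

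The size cannot be fixed from the documents. It rests on assumed new-abnormality rates, pre-dose prevalence and persistence, and runs from modest (2.4 seen as 1.99 at 2% prevalence) to nearly complete loss of the ratio (1.10 at 40%). Prevalence will differ by test.

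A further inference would be that removing pre-existing abnormality lets the open-label percentages be read as a drug effect. It does not: without a control arm, ageing and within-person variation also move normal values out of range. This is a worthwhile and inexpensive improvement to descriptive safety tables, not a defect that invalidates the safety analysis.

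**What to change.** In SAP 4.7:

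1. Replace the plain abnormal counts for laboratory tests, vital signs and ECG category with shift counts from the reference category. Give n (%) newly abnormal (low or high, where that applies) among patients normal at reference, and show patients already abnormal at reference separately.
2. For the open-label phase and the overall study, define the safety reference as the last non-missing value on or before first dose on Day 1.
3. For the randomized-withdrawal comparison by arm, use the last non-missing value on or before the first randomized dose. This is normally Month 12, including for patients who waited for drug supply. Against Day 1, an abnormality that arose in the 12 open-label months would count in either arm.
4. Use the Day 1 pre-dose reference for the laboratory change summaries, in place of the two terms now in that sentence, so that patients who were not rescreened are not omitted. Protocol 10.4 specifies change from screening, so record this as a departure; SAP 1.1 already provides for explaining material departures from the protocol.

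The cost is SAP wording and standard shift-table programming on data already collected. The downside is a smaller denominator. SAP 2.5 implies 220 − 43 − 21 = 156 entrants to the randomized phase, about 78 per arm at 1:1; with an assumed 20% abnormal at reference, about 62 per arm remain (78 × 0.80). The SAP should also say that open-label shift counts are uncontrolled.

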5.1 Efficacy Analysis

General Considerations

Efficacy and biomarker analyses will be based on the FAS analysis set. No adjustments for multiple comparisons will be made. Baseline values for each endpoint are defined as the last non-missing value taken on or prior to Day 1.

Unless otherwise specified, for continuous endpoints that are scheduled to be assessed at only 1 post-baseline visit (MMSE-2), mean changes from baseline will be analyzed using ANCOVA. The analysis will include the categorical, fixed effect of enrollment group (mild vs. moderate AD) along with the continuous, fixed covariate of baseline value of the endpoint being analyzed (baseline). Significance tests comparing endpoint LSMEANS by enrollment group (mild vs. moderate) will be based on least-squares means. Significance of within-group mean changes from baseline will also be reported.

Biomarker exploratory endpoints

Biomarker endpoints to be analyzed may include: 1) CSF Aβ42, 2) CSF tau 3) CSF p- tau181, 4)Version 3.0CONFIDENTIAL, MATERIAL NON-PUBLIC INFORMATIONPage 15 of 19

CSF neurofilament light chain, 5) CSF neurogranin, 6) CSF sTREM2, 7) CSF YKL40 8) CSF HMGB1 9) plasma neurofilament light chain, 10) plasma GFAP, or other non-safety related exploratory biomarkers of disease.

Plasma biomarker data may be analyzed with the MMRM model described above. CSF biomarker data may be analyzed by descriptive statistics.

Note: All biomarker assessments in this study are exploratory endpoints that are not patient safety related; are 'Research Use Only' products; and, hence, are not intended to be compliant with FDA's Quality System Regulation (QSR) or ISO equivalent.

Clinical endpoints

The ADAS-Cog11 will be analyzed using the MMRM model described above. MMSE will be analyzed by ANCOVA.

6 Analysis of Randomized Withdrawal Phase

The following efficacy analyses will be applied to data from the RW phase, which begins after the month 12 assessment and continues through month 18.

These analyses are similar to the analyses from the Open-Label phase except:

- 1) treatment group replaces enrollment group in the analysis models
- 2) baseline value is defined as the last non-missing value at or prior to month 12; or, for patients who were maintained on open-label treatment beyond month 12, baseline is defined as the last non-missing value at or prior to the withdrawal day 1 assessment.

6.1 Efficacy Analysis

General Considerations

The FAS will be the primary data for efficacy analyses.

The primary efficacy estimand for the RW phase is

- Treatment regimen of interest: simufilam treatment for 6 months after OL treatment with simufilam for 12 months vs placebo treatment for 6 months after OL treatment with simufilam for 12 months
- Population:

As defined by inclusion / exclusion criteria

 Variable/Endpoint ADAS-Cog11 • Summary Measure

Difference between treatments in mean change from baseline (month 12) to endpoint (month 18, i.e. month 6 of RW Phase)

• Intercurrent events (ICE) strategy

The primary ICE of interest is early discontinuation of study drug, particularly for lack of efficacy. Given the RW phase is preceded by 12 months of OL treatment with simufilam, most patients entering the RW phase will have already demonstrated tolerability to simufilam; hence, discontinuations due adverse events are expected to be minimal. Discontinuations for lack of efficacy are likely given patients knowledge that the likelihood of being on placebo = 50%.

Discontinuations for lack of efficacy are consistent with a missing at random (MAR) mechanism and therefore a hypothetical strategy is relevant and meaningful. Therefore, a hypothetical strategy will be used to estimate the treatment effect as if the ICE if early discontinuation had not occurred.

Unless otherwise specified, for continuous endpoints that are scheduled to be assessed at > 1 postbaseline visit, mean changes from baseline will be analyzed using a restricted maximum likelihood (REML)-based repeated measures approach (MMRM). The MMRM analysis assumes an MAR mechanism. The analysis will include the categorical, fixed effects of treatment group and Visit, along with the continuous, fixed covariate of baseline value of the endpoint being analyzed (baseline), baseline MMSE score, and the interactions of treatment group, baseline, and baseline MMSE with Visit. An unstructured (co)variance structure will be used to model the within-patient errors. If this analysis fails to converge, the following structures will be tested in this order, with the first structure yielding convergence to be used as the appropriate structure for that variable: heterogeneous Toeplitz (TOEPH), heterogeneous compound symmetric (CSH), and compound symmetric (CS). The Kenward-Roger approximation will be used to estimate denominator degrees of freedom.

Significance tests comparing mean changes from baseline by treatment group will be based on least-squares means. Significance of within-group mean changes from baseline will also be evaluated.

Biomarker Endpoints

Biomarker endpoints to be analyzed may include: 1) CSF A β 42, 2) CSF tau 3) CSF p- tau181, 4) CSF neurofilament light chain, 5) CSF neurogranin, 6) CSF sTREM2, 7) CSF YKL40 8) CSF 1) plasma neurofilament light chain, 2) plasma GFAP.

Plasma biomarker data may be analyzed with the MMRM model described above.

Clinical Endpoints

The ADAS-Cog11 will be analyzed using the MMRM model described above.

7 Analysis of Follow up to Randomized Withdrawal Phase (Openlabel)

The follow up phase is defined as beginning after the month 18 Visit through the month 24 assessment. The following efficacy analyses will be applied to the follow up data.

7.1 Efficacy Analysis

The efficacy analyses will be ADAS-Cog11 using the FAS. The first analysis will be change in ADAS-Cog11 from Month 12 to Month 24 by Treatment, Visit, and mild vs. moderate status. The second analysis will be change in ADAS-Cog 11 from Day 1 to Month 24 by Treatment (i.e. continuous vs. interrupted), Visit, and mild vs. moderate status (mild vs. moderate here based on OL baseline).

The primary comparison of interest from these analyses is the magnitude of the treatment effect at month 18 vs month 24. Maintenance of the treatment effect seen at the end of the RW phase (month 18) throughout the follow up phase (month 24) when all patients are on active drug would be consistent with a disease modifying effect. In contrast, appreciable diminution of the treatment effect when placebo-treated patient switch to active drug would be consistent with a symptomatic treatment effect.

Approvals: 8

[name] Lead Biostatistician **Axiom Real-Time Metrics**

Electronically signed by: [name] Reason: I have reviewed this document Date: Dec 11, 2023 19:14 EST

11-Dec-2023

Date

Electronically signed by: [name] , Reason: I am the Author of [name] this document Date: Dec 11, 2023 11:04 EST

[name] Lead Biostatistician Pentara Corporation

11-Dec-2023

Date

Electronically signed by: [name] Reason: I approve this document Date: Dec 11, 2023 14:29 MST [name] CEO Pentara Corporation

[name]

11-Dec-2023

Date

[name]

[name]

SVP, Neuroscience Cassava Sciences, Inc.

Electronically signed by: [name] Reason: I approve this document Date: Dec 11, 2023 08:46 CST

Electronically signed by: [name] Reason: I have reviewed this

document Date: Dec 11, 2023 09:15 CST

11-Dec-2023

Date

[name] Assistant VP, Clinical Operations Cassava Sciences, Inc.

11-Dec-2023

Date

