• Compare mean changes from baseline on MMSE and ADAS-Cog11 during 24 months of treatment between patients who took simufilam continuously vs those who had interrupted dosing (placebo in the RW phase) (combines data from OL, RW and follow-up phases).

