2.2 Study Design

All patients received simufilam 100 mg b.i.d. as coated oral tablets.

The first 12 months is an open-label treatment of simufilam 100 mg b.i.d. Month 12 to Month 18 is a RW phase in which patients who completed OL treatment are randomized (1:1) to simufilam 100 mg b.i.d. or matching placebo. Month 18 to Month 24 will be an additional 6 months of open-label simufilam 100 mg b.i.d.

Simufilam and placebo will be administered as coated oral tablets. Patients who were enrolled prior to the protocol amendment could continue upon reconsenting to the RW and final 6-month open-label portion.

All patients provided consent to enroll into this study. Patients reported to the clinic in the morning of Day 1. Prior to dosing, patients completed the following baseline measures: ADAS-Cog11, C-SSRS, ECG, vital signs, clinical labs, urinalysis, listen to heart and lungs, and MMSE. A blood sample was collected for plasma-based biomarkers.

Patients returned to the clinic every month through Month 3 and every 1.5 months through Month 12. Visits on Months 4.5, 7.5 and 10.5 included vital signs, listening to heart and lungs, AE monitoring, C-SSRS and drug dispensation and accountability only. Visits at Months 4.5, 7.5 and 10.5 could be performed by telemedicine, based on the judgement of the Investigator. Only AE-monitoring and C-SSRS assessment could be performed remotely. After Month 12, visits occurred on Months 13, 15, 18, 21 and 24. Patients completing Month 12, and who chose to continue into the RW phase of the study, prior to availability of drug supply for the RW phase continued with active treatment until drug supply was ready and therefore had an additional "Withdrawal Day 1" visit before resuming with the Month 13 visit one month later. Collection of saliva for genetic testing occurred at Month 15.

Blood draws for clinical laboratory testing and urine collection for urinalysis were performed at Day 1 and Months 1, 2, 3, 6, 9, 12, 15, 18, 21 and 24. Safety assessments of vital signs and listening to heart and lungs were conducted at Months 2, 4.5, 7.5 and 10.5 visits.

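### The second SAP 7.1 analysis does not condition on the last pre-randomisation ADAS-Cog11, so a chance arm difference from the open-label year carries into both the Month 18 and Month 24 contrasts

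*SAP*

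**What the plan says.** SAP 2.2 sets the order of events. "The first 12 months is an open-label treatment of simufilam 100 mg b.i.d", and only then "patients who completed OL treatment are randomized (1:1) to simufilam 100 mg b.i.d. or matching placebo". Section 6 accordingly resets baseline to Month 12, or to Withdrawal Day 1 for patients kept on open-label drug while supplies were awaited. The repeated-measures model in 6.1 includes "the continuous, fixed covariate of baseline value of the endpoint being analyzed (baseline), baseline MMSE score", each crossed with Visit.

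SAP 7.1 then lists two analyses. "The first analysis will be change in ADAS-Cog11 from Month 12 to Month 24 by Treatment, Visit, and mild vs. moderate status". The other is worded: "The second analysis will be change in ADAS-Cog 11 from Day 1 to Month 24 by Treatment (i.e. continuous vs. interrupted), Visit", with severity taken at the open-label baseline. It serves an exploratory objective in SAP 1.3: "Compare mean changes from baseline on MMSE and ADAS-Cog11 during 24 months of treatment between patients who took simufilam continuously" and those given placebo in the withdrawal phase.

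Section 7.1 names no further covariates. It adds: "The primary comparison of interest from these analyses is the magnitude of the treatment effect at month 18 vs month 24". An effect that persists is read as consistent with disease modification, and one that shrinks as consistent with a symptomatic effect. The two analyses are not ranked for this purpose.

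**The concern.** The continuous and interrupted arms do not exist until randomisation after Month 12. Change from Day 1 to Month 18 or 24 is the open-label change plus the change since randomisation. The first part cannot differ between arms because of treatment, but with finite arms it differs by chance.

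Unless the model conditions on the score at randomisation, that chance difference stays in the arm contrast at every later visit, with the same sign. Two things are at stake. Each visit's contrast is noisier than it need be. The noise is also shared between Months 18 and 24, so a chance imbalance tends to give similar apparent effects at both visits, which is the pattern 7.1 reads as disease modification.

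**Working it through.** **Text check.** There are three ways to read the second analysis.

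1. Only the listed terms are fitted. The Month 12 score is then absent.
2. The 6.1 covariates carry over. For change from Day 1, the endpoint's baseline is the Day 1 score, so Month 12 is still absent.
3. Month 12 enters as one more outcome visit with free Treatment-by-Visit means. With complete data, the Month 18 and 24 contrasts are still not conditioned on it.

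**Inputs.** The documents give no SD, effect size or power for this comparison, so there is no planned figure to reproduce. From SAP 2.5: 220 - 43 - 21 = 156, at most 78 per arm. Everything else is assumed: a random intercept and slope model with intercept SD a = 6 or 8, slope SD b = 3 or 5 points/year, visit error SD e = 2.5 or 3.5, and intercept-slope correlation 0 or 0.3. That makes 16 combinations.

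**Chance imbalance in Day 1 to Month 12 change.** SE = sqrt[(2/78)(b² + 2e²)].
- Smallest: sqrt[(2/78)(9 + 12.5)] = 0.74 points.
- Largest: sqrt[(2/78)(25 + 24.5)] = 1.13 points.
- The chance of an imbalance above 1 point is 18% to 37%.

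**Contrast SE.** SE = sqrt[(2/78) × residual variance given the covariates]. With zero correlation and time in years, Var(Y_t) = a² + t²b² + e² and Cov(Y_s, Y_t) = a² + stb².

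Worked case, a = 6, b = 3, e = 2.5, correlation 0:
- Conditioning on Day 1 subtracts 36²/42.25 = 30.67 from each later variance and covariance.
- Month 18 given Day 1: 62.50 - 30.67 = 31.83, SE 0.90.
- Month 24 given Day 1: 78.25 - 30.67 = 47.58, SE 1.10.
- Their covariance is 63 - 30.67 = 32.33, so the correlation is 32.33/sqrt(31.83 × 47.58) = 0.83.
- Adding Month 12, whose variance given Day 1 is 51.25 - 30.67 = 20.58: Month 18 becomes 31.83 - 18.83²/20.58 = 14.60, SE 0.61. Month 24 becomes 47.58 - 23.33²/20.58 = 21.13, SE 0.74. The covariance becomes 10.98 and the correlation 0.63.
- Month 24 minus Month 18: Day 1 only, 31.83 + 47.58 - 2 × 32.33 = 14.75, SE 0.61. With Month 12, 14.60 + 21.13 - 2 × 10.98 = 13.77, SE 0.59.

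Over all 16 combinations:

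| Quantity | Day 1 only | Day 1 and Month 12 |
|---|---|---|
| SE, Month 18 | 0.90-1.44 | 0.61-0.89 |
| SE, Month 24 | 1.10-1.78 | 0.72-1.09 |
| Correlation of the two null contrasts | 0.74-0.92 | 0.55-0.70 |
| SE, Month 24 minus Month 18 | 0.61-0.89 | 0.59-0.84 |

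The single-visit SE ratio is 1.30-2.02. About 40-75% of the variance of the Day 1-adjusted contrast is removed by adding Month 12. For the difference between visits, the SE is only 1-14% larger.

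**Simulation.** There were 6,000 runs per scenario, with 78 per arm, intercept SD 7, slope SD 4-6, error SD 2.5-3, no dropout, and single-visit least squares with severity in every model. With no drug effect:
- The Day 1-based contrast averages about zero and rejects in 4.6-5.0% of trials at each visit.
- Given a Month 12 imbalance near 1.5 points, it shows 1.5-1.7 points at Month 18 and 1.9-2.3 at Month 24. Conditioning on Month 12 leaves about 0 to 0.2.
- Significance at both visits in the same direction occurs in 2.6-3.1% of trials, against 1.4-1.6% with conditioning.

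For an assumed true effect of 2 points (slope SD 5, error SD 3), power is about 30% at Month 18 and 21% at Month 24 without Month 12. With it, power is about 70% and 51-53%.

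**The case against.** The strongest reply is that 7.1 already contains an analysis that starts at randomisation, that the primary withdrawal-phase contrast in 6.1 is also based on Month 12, and that change from Day 1 is the natural scale for an exploratory 24-month objective. All of that stands. It limits the point to one of two follow-up analyses, but does not supply the missing covariate in that one.

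Several stronger readings are tempting, and the documents do not support them.

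- A reader might infer that 7.1 as a whole ignores the time of randomisation. It does not, because the first analysis measures change from Month 12.
- A reader might infer that the 12 months of open-label change is itself counted as treatment effect. That change is common to both arms and cancels in expectation. Only the chance arm difference in it remains.
- A reader might infer bias or an inflated error rate. Randomisation keeps the contrast unbiased on average, and the simulated per-visit error is about 5%.
- A reader might apply the 1.3- to 2.0-fold loss to the comparison of Month 18 with Month 24. In the direct difference most of the shared noise cancels, leaving 1-14%. However, 7.1 specifies no test of that difference. It compares the size of the effect at each visit, and those sizes are what a Month 12 imbalance distorts.
- A reader might say that the first analysis drops its baseline covariate. Section 7.1 is silent there, and the 6.1 default for endpoints with several post-baseline visits plausibly fills the gap. The same default does not help the second analysis, where it supplies the Day 1 score.

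**Conclusion.** The point holds for the second 7.1 analysis only. It is a loss of precision, with noise shared between two visits whose similarity is to be interpreted. It is not average bias. The text supports it under every reading of the model.

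The sizes rest on assumed SDs, a linear random-slope model, no dropout after Month 12, and 78 per arm, which is the most that SAP 2.5 allows. Different SDs would move the figures. The direction would stay the same as long as the Month 12 score predicts later scores beyond what Day 1 does.

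The change should be made: the loss at each visit is material, a mechanistic reading depends on it, and the remedy needs no new data. No primary result is affected.

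**What to change.** In SAP 7.1, state for the second analysis that the arm contrasts are estimated from post-randomisation visits (Months 13 to 24), with the randomised-withdrawal baseline ADAS-Cog11 as defined in section 6 (Month 12 or Withdrawal Day 1) by Visit as a covariate, alongside Day 1 ADAS-Cog11 by Visit. Keep change from Day 1 as the scale for displaying least-squares means. An equivalent choice is one longitudinal model with arm means constrained to be equal at every visit up to randomisation, including Withdrawal Day 1 where it applies.

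For the first analysis, confirm in a few words that the 6.1 baseline-by-Visit covariate applies. That is a clarification only.

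The cost is a sentence of SAP text and a few lines of code. Section 6 already defines the variable, and the full analysis set, which SAP 3.2 defines for each phase, already requires a baseline record. SAP 1.2 says that earlier SAP versions were used for the open-label and withdrawal analyses, so the covariate is better fixed in writing than left to be chosen at the final analysis.
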